2.3.3. Benefit Assessment

Personalized medicine in OA is emerging, as it is unlikely that one single treatment will have an effect in all patients due to the heterogeneity of the disease. Previous trials have shown possible effects of biological anti-inflammatory drugs on reducing joint damage in hand OA (8), but disappointing effect on symptoms (10). To avoid failures of future OA trials, the heterogeneity of the disease must be acknowledged. The involvement of various tissues will differ across patients and at different disease stages. Further, pain is strongly influenced by genetic predisposition, psychological and social factors and differences in the pain processing system, which may affect the treatment responses. There are reasons to believe that some phenotypes may benefit from anti-inflammatory treatments, whereas others may benefit from therapies directed at bone or cartilage, central sensitization or cognitive aspects.

In clinical practice, MTX is occasionally used off-label in OA patients with unmanageable pain and inflammation, but the practice is currently not evidence-based. Previous studies (mainly open-label) have indicated a symptomatic effect in patients with knee and hand OA (11-13), but high-quality RCTs are needed to provide clear evidence in support of or against current practice. A small (n=30) open-label trial found \geq 30% reduction in VAS pain in 43% of the knee OA participants given MTX, suggesting an analgesic efficacy (11). A recent small RCT of persons with erosive hand OA (n=64) showed a positive trend with larger pain relief in patients treated with MTX vs. placebo after 3 months (decrease of mean (standard deviation; SD) visual analogue scale (VAS) pain: 17.5 (28.4) vs. 8.4 (25.3); p=0.18) (14). However, the lack of inflammation in the majority of patients and the low dose of MTX (10 mg/week) make us unable to draw firm conclusions about its efficacy. Interestingly, fewer patients developed new erosions in the MTX vs. placebo arm (8% vs. 29%; p=0.09), suggesting a disease-modifying effect.

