6.3. Assignment to Study Intervention

The treating physician will decide, based on best clinical practice, if the patient should try MTX after the MERINO-trial. Central to this approach is the collaborative effort between the physician and participant, fostering an environment where patient perspectives are integral to treatment decisions. It will be emphasized by the physician prescribing MTX open-label that this is not evidence-based treatment until results of the MERINO-trial are published. We do, however, justify the continuation of MTX based on recent results from the METHODS trial (5). In the cases where the physician finds an indication for trying MTX after the MERINO trial, usual practice would be to try MTX for three months and then evaluate whether the patient should continue the treatment or not, based on synovitis scores and self-reported effects.

As described in section 5, this result in four groups in the MERINO:2 study, but since MTX treatment length and MTX doses could vary substantial in the observational time of the MERINO:2 study, we will adjust for this in the analyses.

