6.4. Blinding

This is an open-label study; potential bias will be reduced by blinding the researcher who will interpret and score the radiographs.

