9.1. Statistical Hypotheses

The primary objective is to demonstrate that MTX is superior to treatment as usual in achieving slower radiographic progression at 30 months. Thus, the null hypothesis to be tested in relation to the primary estimand is as follows:

• Null hypothesis: MTX treatment for 30 months is not different from placebo (12 months) and subsequent treatment as usual (18 months) with respect to the progression of Verbruggen-Veys scoring system in participants with erosive hand OA.

VS.

• Alternative hypothesis: MTX treatment for 30 months is different from placebo (12 months) and subsequent treatment as usual (18 months) with respect to the progression of Verbruggen-Veys scoring system in participants with erosive hand OA.

Secondary outcomes (1):

- Null hypothesis: MTX treatment for 30 months is not different from placebo (12 months) and subsequent treatment as usual (18 months) with respect to the progression of KL scale or OARSI atlas in participants with erosive hand OA.
- Alternative hypothesis: MTX treatment for 30 months is different from placebo (12 months) and subsequent treatment as usual (18 months) with respect to the progression of KL scale or OARSI atlas in participants with erosive hand OA.

Secondary objective (2)

- Null hypothesis: MTX is not different from placebo/treatment as usual with respect to change from baseline to 12/30 months in OMERACT-OARSI responder criteria, AUSCAN or EQ-5D-5L.
- Alternative hypothesis: MTX is different from placebo/treatment as usual with respect to change from baseline to 12/30 months in OMERACT-OARSI responder criteria, AUSCAN or EQ-5D-5L.

Multiplicity control is not relevant for the study.

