9.3. Statistical Analyses

Continuous variables will be subject to linear mixed models. Binary response variables will be analyzed using logistic regression models (possibly adjusting for within-subject dependencies by mixed model approaches). Analyses at the joint level will apply generalized estimating equations (GEE) to account for dependency between joints within one person. The SAP will detail these procedures.

The hypotheses will be evaluated by the p-value associated with the between group difference at study end. A conclusion of superiority will be made if the null hypothesis is rejected on an overall significance level of 5%. The SAP will detail these procedures, as well as alternative and further supportive evaluations, such as analyses including unbalanced baseline predictors or modifications of the linear regression model in case validity assumptions are not met.

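### Section 9.3 allows a superiority conclusion on month-30 patient-reported outcomes, although that open-label, non-randomised contrast cannot separate an MTX effect from expectation, loss of placebo response or self-selection

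*Protocol*

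**What the plan says.** **Hypothesis.** Protocol Section 9.1, secondary objective (2), has as its null: "MTX is not different from placebo/treatment as usual with respect to change from baseline to 12/30 months in OMERACT-OARSI responder criteria, AUSCAN or EQ-5D-5L". The primary and first secondary hypotheses in the same section write the comparator out as a sequence: "MTX treatment for 30 months is not different from placebo (12 months) and subsequent treatment as usual (18 months"). Hypothesis (2) does not.

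**Decision rule.** Section 9.3: "The hypotheses will be evaluated by the p-value associated with the between group difference at study end". It continues: "A conclusion of superiority will be made if the null hypothesis is rejected on an overall significance level of 5" per cent. No hypothesis is exempted.

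**Blinding.** Section 6.4: "This is an open-label study; potential bias will be reduced by blinding the researcher who will interpret and score the radiographs". No other bias control is stated.

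**Treatment after month 12.** Section 6.3: "The treating physician will decide, based on best clinical practice, if the patient should try MTX after the MERINO-trial". The same section says that MTX is usually tried for three months and continued or stopped on synovitis scores and the patient's own report of effect.

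**Baseline.** Section 8 takes the MERINO month-12 data as the baseline for MERINO:2.

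**Only placebo-arm change in the protocol.** Section 2.3.3 cites a small randomised trial in erosive hand osteoarthritis (n=64) with three-month falls, MTX versus placebo, in "visual analogue scale (VAS) pain: 17.5 (28.4) vs. 8.4 (25.3); p=0.18".

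**The concern.** AUSCAN and EQ-5D-5L are questionnaires. The OMERACT-OARSI response is computed from AUSCAN pain and function and the patient's global assessment. The VAS endpoints in Table 1 are also self-reported. A blinded radiograph reader protects none of these.

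At month 30 the groups differ in more than the drug. One group knows it takes MTX. The other has come off placebo and knows it receives usual care. Who is in which group was settled by physician and participant, and staying on MTX depends partly on how the patient says it works. Expectation, loss of placebo response and self-selection all enter the same between-group difference as any drug effect, and the p-value cannot tell them apart.

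Section 9.3 nevertheless gives a significant result the label of superiority. At stake is a claim of long-term symptomatic benefit, authorised in advance, that the data could not support.

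**Working it through.** The protocol gives no effect size, SD or power for this hypothesis, and Section 9.5 says the sample size has no statistical basis. There is no design figure to reproduce. The calculation below illustrates one mechanism, loss of placebo response in controls.

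**Inputs**
- Falls in VAS pain of 17.5 (SD 28.4) on MTX and 8.4 (SD 25.3) on placebo (Section 2.3.3; another trial, 3 months).
- 153 potential participants and four groups (Sections 1.1 and 5).
- Assumed: equal groups, so 153/4 ≈ 38 each, or 25 each with incomplete attendance; true drug effect zero; MTX users keep their response; controls lose L = 25%, 50% or 100% of 8.4 mm, that is 2.1, 4.2 or 8.4 mm.

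**Check on the borrowed figures.** Assuming 32 per arm, SE = √(28.4²/32 + 25.3²/32) = 6.72, t = (17.5 − 8.4)/6.72 = 1.35, p = 0.18. This agrees with the cited value.

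**Chance of a false result favouring MTX**

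Pooled SD = √((28.4² + 25.3²)/2) = 26.9. SE = 26.9 × √(2/n), which is 6.17 at n = 38 and 7.61 at n = 25.

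P = 1 − Φ(1.96 − L/SE). With L = 0 this is 2.5%.

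| L (mm) | n = 38 | n = 25 |
|---|---|---|
| 2.1 (25%) | 5.3% | 4.6% |
| 4.2 (50%) | 10.0% | 8.0% |
| 8.4 (100%) | 27.5% | 19.6% |

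The choice of SD matters little. At n = 38 and the same three losses, SD 25.3 gives 5.5%, 10.8% and 30.4%; SD 28.4 gives 5.1%, 9.4% and 25.1%.

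**Does naming the comparator separately at each time point remove the problem?** No. With a month-0 baseline, the month-30 contrast is the drug effect plus L. With the month-12 baseline of Section 8, an effect already present at month 12 cancels, and the contrast is L plus any later drug effect. L stays in both. At n = 38, SD 25.3 and L = 8.4 mm the false-positive chance is 30% with or without the split. Only the month-12 contrast against placebo stays at 2.5%.

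**Baseline wording.** If month 12 is the baseline, change from baseline to month 12 is zero by definition. Hypothesis (2) must therefore mean another baseline at least for month 12, and it does not say which.

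**The case against.** **The study declares itself open-label, and every such study has this limitation.** True, and the design is not the complaint. The point is the conclusion that Section 9.3 attaches to it.

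**Superiority is an aim only for radiographs.** Sections 1.1 and 9.1 do use the word only for radiographic progression, the symptom hypotheses are worded as a difference, and Section 3 speaks of exploring. This weakens the point. It does not remove it, because the rule in 9.3 refers to the hypotheses without exception. Nor is this a detail left to the statistical analysis plan: the protocol itself fixes both the hypothesis and the rule.

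**Stronger readings a reader might infer, which the documents do not support**
- *That placebo and usual care are pooled into one control, and that this creates the bias.* The two slashes in hypothesis (2) can equally mean placebo at month 12 and usual care at month 30, which fits the schedule and the other hypotheses. The wording is ambiguous, not a clear pooling, and the bias survives separation.
- *That the bias favours MTX.* Retaining MTX users who report benefit would push that way. But MTX is used off-label for unmanageable pain and inflammation, so worsening placebo participants may move to MTX and leave milder cases on usual care. If the planned intervention in Section 9.2 means the randomised arm, switchers would dilute the contrast.
- *That the protocol shows how large the loss would be.* It gives one placebo-arm change, from another trial, at three months, on a scale that hypothesis (2) does not name, and including natural course. No figure supports any share lost.
- *That the radiographic endpoints are safe because the reader is blinded.* Post-month-12 treatment is not randomised for them either.

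**Conclusion.** The concern holds as a fault in the decision rule. Section 9.3 would label a significant month-30 difference on patient-reported outcomes as superiority, when the contrast cannot separate an MTX effect from expectation, loss of placebo response or self-selection.

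The exposure is greatest for MTX throughout versus placebo then usual care, which Section 4.1 singles out as of special interest. That MERINO's placebo was blinded is implied by the placebo control and the blind-break wording in Appendix 4, not stated outright.

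The net direction and size are unknown. The figures of 5.3% to 27.5% at 38 per group show only that a modest loss of response in controls could matter. At a 25% loss the excess over 2.5% is under 3 percentage points, and 100% is an upper bound on the loss because part of the 8.4 mm is natural course or regression to the mean. Self-selection is not modelled. These are secondary endpoints, but the change affects what the study may conclude.

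**What to change.** **Section 9.3 (the essential change).** Exclude month-30 patient-reported outcomes from the superiority rule. Report them as estimates with 95% confidence intervals, labelled open-label and non-randomised. Beside them show the month 12 to month 30 change in the placebo-to-treatment-as-usual group, so that readers can see how much of the difference arises after placebo ends.

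**Section 9.1 (clarification).** For hypothesis (2), state the comparator and baseline at month 12 and at month 30, and reconcile this with the month-12 baseline in Section 8. This alone would not cure the problem.

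The revised text should not say that reader blinding by itself justifies a superiority conclusion for the radiographic endpoints.

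**Cost.** Wording in two sections and one descriptive table from data already collected. The sponsor gives up a superiority claim on symptoms at month 30.

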9.2. Analysis Sets

| Participant Analysis Set | Description |
|---------------------------|---|
| Full analysis set (FAS) | All randomized participants. |
| Safety analysis set (SAS) | All participants who are exposed to investigational intervention. |

For the purposes of analysis, the following analysis sets are defined:

The full analysis set will be used to analyze endpoints related to the efficacy objectives and the safety analysis set will be used to analyze the endpoints and assessments related to safety.

For the efficacy analyses, participants will be included in the analyses according to the planned investigational intervention; whereas for safety analyses, participants will be included in the analyses according to the investigational intervention they actually received.

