All participants recruited to the MERINO trial will be asked to provide conventional radiographs and electronic questionnaires 30 months after starting the MERINO trial. This results in four potential arms of the MERINO:2 trial, depending on the two former arms of the MERINO trial, each with a duration of 12+18=30 months:

- MTX \rightarrow MTX
- MTX \rightarrow Treatment as usual
- Placebo \rightarrow MTX
- Placebo \rightarrow Treatment as usual

Data Monitoring/Other Committee: No

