6.1. Study Intervention Administered

Study intervention is defined as any investigational intervention(s), marketed product(s), or placebo intended to be administered to a study participant according to the study protocol (Table 3).

| ARM Name | Intervention | Co-medication |
|-------------------------|--|--|
| Intervention Name | МТХ | Folic acid |
| Producer | Pfizer | Orifarm Generics (Orifarm Healthcare AS) |
| ATC | L04A X03 | B03B B01 |
| Туре | Drug | Drug |
| Dose Formulation | Tablet | Tablet |
| Box size | 206 (x2) | 100 |
| Unit Dose Strength(s) | Methotrexate 2.5mg | 1mg |
| Frequency | Weekly | Daily |
| Dosage Level(s) | Decided by the treating physician, usually 10- 20mg weekly, with a down-scaled dose the first 2-3 weeks. | 1mg x 1 |
| Route of Administration | Oral | Oral |
| Use | Intervention | Minimize expected adverse reactions to methotrexate |
| IMP and NIMP | IMP | NIMP |
| Sourcing | Provided by local pharmacy | Provided by local pharmacy |
| Packaging and Labeling | Provided by local pharmacy according to national routines. | Provided by local pharmacy according to national routines. |

Table 3. Study interventions

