8.4.1. Time Period and Frequency for Collecting AE and SAE Information

All SAEs will be collected from the signing of the informed consent form until the scheduled 30month visit (after entering the MERINO trial). Medical occurrences that begin before the start of study intervention but after obtaining informed consent will be recorded as medical history/current medical conditions, not as AEs.

All SAEs will be recorded and reported to the sponsor or designee immediately and under no circumstance should this exceed 24 hours, as indicated in Appendix 3. The investigator will submit any updated SAE data to the sponsor within 24 hours of it being available.

Investigators are not obligated to actively seek information on AEs or SAEs after conclusion of the study participation. However, if the investigator learns of any SAE, including a death, at any time after a participant has been discharged from the study, and the investigator considers the event to be reasonably related to the study intervention or study participation, the investigator must promptly notify the sponsor.

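### The safety set in 9.2 names neither the product nor the period that counts as exposure; read with MTX as the product, it leaves safety reporting without a never-MTX reference and books off-drug time as MTX time

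*Protocol*

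**What the plan says.** Section 9.2 defines the safety analysis set as "All participants who are exposed to investigational intervention". It states that "the safety analysis set will be used to analyze the endpoints and assessments related to safety", and that "for safety analyses, participants will be included in the analyses according to the investigational intervention they actually received". No product and no exposure period are given.

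The related provisions are these:

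- Section 6.1: "Study intervention is defined as any investigational intervention(s), marketed product(s), or placebo intended to be administered to a study participant". Table 3, directly below, labels MTX as IMP and folic acid as NIMP, and lists nothing else.
- Synopsis: "This results in four potential arms of the MERINO:2 trial", formed by MTX or placebo in MERINO followed by MTX or treatment as usual.
- Section 8.4.1: "All SAEs will be collected from the signing of the informed consent form until the scheduled 30month visit". The next sentence sends events that arise after consent but before study intervention starts to medical history rather than to AEs.
- Appendix 3 (10.3.1) ties an AE in time to use of the study intervention.
- Section 6.3 describes a usual three-month trial of MTX followed by a decision to continue or stop, and promises in general terms to adjust for length and dose.

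**The concern.** The study sets MTX against treatment as usual, and one of its four groups never receives MTX: placebo followed by usual care. A safety set built on exposure to the investigational product is the usual choice in a trial where every arm is dosed. Here it can remove the only group that shows how often serious events occur in these patients without the drug. Hospital admissions and other SAEs also occur in adults with hand osteoarthritis who do not take MTX, so without that group an MTX count cannot be set against a background.

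The second difficulty is time. SAE collection runs to month 30 whatever the participant is taking. A person-level label based on treatment received assigns the whole period to MTX even if the drug was stopped early, and this dilutes any MTX-related rate.

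**Working it through.** The protocol gives no safety sample size, event rate or other safety figure, so there is no number to reproduce. The check is a reading of the definition, followed by an illustrative head-count.

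**Inputs from the protocol.** 153 potential participants (Synopsis, 9.5); 12 + 18 = 30 months (Synopsis); MTX as the only IMP (Table 3); a three-month trial of MTX as usual practice (6.3).

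**Assumptions, not in the protocol.** Equal MERINO arms, 153 / 2 = 76.5 each; everyone takes part; the same share q of each former arm takes MTX for all of months 12 to 30, with q = 0.25, 0.50 or 0.75.

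**Group sizes.** MTX→MTX and placebo→MTX: 76.5q each. MTX→usual care and placebo→usual care: 76.5(1 − q) each.

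**Three readings of exposure.**

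- A, ever on MTX: set = 76.5(1 + q); dropped (placebo→usual care) = 76.5(1 − q); off-drug share of months 12 to 30 within the set = (1 − q)/(1 + q).
- B, on MTX during MERINO:2: set = 153q; dropped (both usual-care groups) = 153(1 − q).
- C, placebo also counts: set = 153; dropped = 0.

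| q | A: set | A: dropped | A: off-drug share | B: set | B: dropped | C: dropped |
|---|---|---|---|---|---|---|
| 0.25 | 95.6 | 57.4 | 0.75/1.25 = 60% | 38.25 | 114.75 | 0 |
| 0.50 | 114.75 | 38.25 | 0.50/1.50 = 33% | 76.5 | 76.5 | 0 |
| 0.75 | 133.9 | 19.1 | 0.25/1.75 = 14% | 114.75 | 38.25 | 0 |

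Reading A retains an off-drug group (MTX→usual care), but it is previously exposed. Reading B retains no usual-care group. Only reading C retains people who never took MTX.

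**Off-drug time in one participant.** Someone who starts MTX at month 12 and stops after three months is off drug for 18 − 3 = 15 of 18 months, 15/18 = 83%. This applies under A, B and C, because 9.2 sets no rule for time after stopping. The SAE window opens at MERINO:2 consent, which the Schedule of Activities places somewhere in months 12 to 30. For this participant, later consent removes on-drug time first, so the off-drug share of the window is at least 83%.

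**The case against.** The strongest reply is that reading C may be intended. Section 6.1 names placebo within study intervention, and the efficacy sentence of 9.2 places all randomised participants, placebo arm included, under a planned investigational intervention. A rule that groups people by what they received also implies more than one group. This stands as a real ambiguity. It does not settle the matter, because 9.2 uses the narrower term, 6.1 lists placebo separately from investigational interventions, and Table 3 gives MTX alone as IMP.

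Several stronger readings are tempting and are not supported:

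- A reader might infer that 9.2 keeps people whose MTX ended before MERINO:2. That requires reading A; under B they are excluded.
- A reader might infer that an SAE-rate comparison is planned and lacks its control. The protocol states no safety objective, endpoint or hypothesis, and person-time methods may properly sit in the SAP. The harm is to the interpretability of safety reporting, not to a test.
- A reader might infer that collected SAEs are discarded. Section 9 says analysis and reporting cover all data from all participants, so exclusion from one set does not mean non-reporting.
- A reader might infer that the data for a complete comparison are certain to exist. The medical-history sentence in 8.4.1 and the AE definition in Appendix 3 leave it unclear whether events in people who never start MTX are recorded as SAEs at all.

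Section 6.3 does promise adjustment for MTX length and dose, but does not connect it to safety.

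**Conclusion.** The point holds as a defect in a rule that the protocol itself fixes. Both readings that take MTX as the investigational product lose the never-MTX reference, against planned SAE collection from every consented participant. Under all three readings, grouping by treatment received with no time rule mixes on-drug and off-drug months.

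The size depends on uptake, which is unknown. Under the ever-MTX reading about 57 to 19 participants are dropped and 60% to 14% of the set's time in months 12 to 30 is off drug; the number dropped is zero if placebo counts. These figures rest on full participation of 153, equal arms and uniform uptake of 25% to 75%. Participation is voluntary and 153 is MERINO's recruitment target, so actual counts may be lower. The 83% figure needs only the three-month stop described in 6.3, a start at month 12 and the 18-month period. The correction should be made before database lock; no stated number in the protocol is wrong on this point.

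**What to change.** In 9.2:

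1. Define the safety set as all consented MERINO:2 participants.
2. Classify each SAE by MTX exposure at its onset, using the questionnaire and prescription-database data already planned in 4.3 and 6.5, and define the on-drug window.
3. Use person-time from MERINO:2 consent to month 30, the period in which SAEs are collected, and not all of months 12 to 30.
4. Show the four groups descriptively beside the on-drug and off-drug tabulation.

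In 8.4.1 and Appendix 3, reconcile the wording so that a serious event in a participant who never starts MTX is recorded as an SAE and not as medical history.

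The cost is a short edit in three places, a slightly larger table and some exposure-coding work. No new participant procedures are needed. The resulting comparison is non-randomised, because the treating physician and the participant choose the treatment, and it should be presented as descriptive.
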